9.4.10 Drug Supplies and Accountability

In compliance with local regulatory requirements, drug supplies will not be sent to the investigator until the following documentation has been received by the sponsor:

- A signed and dated confidentiality agreement
- A copy of the final protocol signature page, signed and dated by both the sponsor and investigator
- Written proof of approval of the protocol, the ICFs, and any other information provided to the subjects by the IRB/IEC for the institution where the study is to be conducted
- A copy of the IRB/IEC-approved ICF and any other documentation provided to the subjects to be used in this study

- The IRB/IEC membership list and statutes or Health and Human Services Assurance number
- A copy of the certification and a table of the normal laboratory ranges for the reference laboratory conducting the clinical laboratory tests required by this protocol
- An investigator-signed and dated Food and Drug Administration (FDA) Form FDA 1572, where applicable
- Financial Disclosure form(s) for the principal investigator (PI) and all subinvestigators listed on Form FDA 1572, where applicable
- A signed and dated curriculum vitae (CV) of the PI including a copy of the PI's current medical license or medical registration number on the CV
- A signed and dated clinical studies agreement

The investigator and the study staff will be responsible for the accountability of all study drugs/study supplies (dispensing, inventory, and record keeping) following the sponsor's instructions and adherence to Good Clinical Practice (GCP) guidelines as well as local or regional requirements.

Under no circumstances will the investigator allow the study drugs/study supplies to be used other than as directed by this protocol. Study drugs/study supplies will not be dispensed to any individual who is not enrolled in the study.

The site must maintain an accurate and timely record of the following: receipt of all study drugs/study supplies, dispensing of study drugs/study supplies to the subject, collection and reconciliation of unused study drugs/study supplies that are either returned by the subjects or shipped to site but not dispensed to subjects, and return of reconciled study drugs/study supplies to the sponsor or (where applicable) destruction of reconciled study drugs/study supplies at the site. This includes, but may not be limited to: (a) documentation of receipt of study drugs/study supplies, (b) study drugs/study supplies dispensing/return reconciliation log, (c) study drugs/study supplies accountability log, (d) all shipping service receipts, (e) documentation of returns to the sponsor, and (f) certificates of destruction for any destruction of study drugs/study supplies that occurs at the site. All forms will be provided by the sponsor. Any comparable forms that the site wishes to use must be approved by the sponsor.

The study drugs/study supplies and inventory records must be made available, upon request, for inspection by a designated representative of the sponsor or a representative of a health authority (eg, FDA, MHRA). As applicable, all unused study drugs/study supplies and empty and partially empty containers from used study drugs/study supplies are to be returned to the investigator by the subject and together with unused study drugs/study supplies that were shipped to the site but not dispensed to subjects are to be returned to the sponsor's designated central or local depot(s) during the study or at the conclusion of the study, unless provision is made by the sponsor for destruction of study drugs/study supplies and containers at the site. Destruction at the site will only occur under circumstances where regulation or supply type prohibits the return of study drugs/study supplies to the central or local depot(s).

Approval for destruction to occur at the site must be provided by the sponsor in advance. Upon completion of drug accountability and reconciliation procedures by the site's personnel and documentation procedures by the sponsor's personnel, study drugs/study supplies that are to be returned to the sponsor's designated central or local depot(s) must be boxed and sealed and shipped back to the central or local depot(s) following all local regulatory requirements. In some regions, study drugs/study supplies may be removed from the site and hand delivered to the central or local depot by sponsor representatives. Where study drugs/study supplies are approved for destruction at the site, destruction will occur following the site's standard procedures and certificates of destruction will be provided to the sponsor.

Drug accountability will be reviewed during site visits and at the completion of the study.

9.5 Study Assessments

- 9.5.1 Assessments
- 9.5.1.1 Demography

Subject demographic information will be collected at the Screening Visit. Demographic information includes date of birth (or age), sex, race/ethnicity, and BMI.

- 9.5.1.2 Baseline Assessments
- 9.5.1.2.1 MEDICAL HISTORY

Medical and surgical history and current medical conditions will be recorded at the Screening Visit. All clinically significant medical and surgical history must be noted in the Medical History and Current Medical Conditions CRF.

9.5.1.2.2 HEIGHT AND WEIGHT MEASUREMENTS

Height (cm) and weight (kg) will be recorded and BMI will be determined at the Screening Visit. Subjects will have their weight (kg) measured again on Day -1.

9.5.1.3 Efficacy Assessments

Not applicable.

- 9.5.1.4 Pharmacokinetic, Pharmacodynamic, Pharmacogenomic, and Other Biomarker Assessments
- 9.5.1.4.1 PHARMACOKINETIC ASSESSMENTS

Plasma concentration of Lemborexant

Blood samples (4 mL each) will be collected as specified in the Schedule of Procedures/Assessments (Table 4). A separate lab manual will be provided for a description of collection, handling, and shipping procedures of the plasma samples for PK analysis. In

addition, blood samples for protein binding (12 mL per time point) of lemborexant will be collected at 1 and 24 hours postdose matching the PK sample collection at those time points.

Total plasma concentrations of lemborexant and its metabolites (M4, M9, and M10) will be measured by validated liquid chromatography with tandem mass spectrometry (LC-MS/MS) methods. The unbound concentrations of lemborexant, M4, M9, and M10 will also be measured using a similar validated LC-MS/MS method following equilibrium dialysis.

9.5.1.4.2 PHARMACODYNAMIC, PHARMACOGENOMIC, AND OTHER BIOMARKER ASSESSMENTS

Not applicable.

9.5.1.5 Safety Assessments

Safety assessments will consist of monitoring and recording all AEs and SAEs; regular monitoring of hematology, blood chemistry, and urine values; periodic measurement of vital signs and ECGs; and performance of physical examinations as detailed in Table 4.

9.5.1.5.1 **ADVERSE EVENTS**

An AE is any untoward medical occurrence in a patient or clinical investigation subject administered an investigational product. An AE does not necessarily have a causal relationship with the medicinal product. For this study, the study drug is lemborexant.

The criteria for identifying AEs in this study are:

- Any unfavorable and unintended sign (including an abnormal laboratory finding), symptom, or disease temporally associated with the use of an investigational product, whether or not considered related to the investigational product. Note: Every sign or symptom should not be listed as a separate AE if the applicable disease (diagnosis) is being reported as an AE
- Any new disease or exacerbation of an existing disease
- Any deterioration in non-protocol required measurements of a laboratory value or other clinical test (eg, ECG or x-ray) that results in symptoms, a change in treatment, or discontinuation of study drug
- Recurrence of an intermittent medical condition (eg, headache) not present pretreatment (Baseline)
- An abnormal laboratory test result should be considered an AE if the identified laboratory abnormality leads to any type of intervention, withdrawal of study drug, or withholding of study drug, whether prescribed in the protocol or not.

All AEs observed during the study will be reported on the CRF. All AEs, regardless of relationship to study drug or procedure, should be collected beginning from the time the subject signs the study ICF through the last visit in the Treatment Phase and for 28 days after the subject's last dose. Serious AEs will also be collected for 28 days after the last dose (or 5 times the half-life, whichever is longer).

Abnormal laboratory values should not be listed as separate AEs if they are considered to be part of the clinical syndrome that is being reported as an AE. It is the responsibility of the investigator to review all laboratory findings in all subjects and determine if they constitute an AE. Medical and scientific judgment should be exercised in deciding whether an isolated laboratory abnormality should be classified as an AE. Any laboratory abnormality considered to constitute an AE should be reported on the Adverse Event CRF.

All AEs must be followed for 28 days (or $5 \times$ the half-life, whichever is longer) after the subject's last dose, or until resolution, whichever comes first. All SAEs must be followed to resolution or, if resolution is unlikely, to stabilization.

Every effort must be made by the investigator to categorize each AE according to its severity and its relationship to the study treatment.

Assessing Severity of Adverse Events

AEs will be graded on a 3-point scale (mild, moderate, severe) and reported in the detail indicated on the CRF. The definitions are as follows:

- Mild Discomfort noticed, but no disruption of normal daily activity
- Moderate Discomfort sufficient to reduce or affect normal daily activity
- Severe Incapacitating, with inability to work or to perform normal daily activity

The criteria for assessing severity are different than those used for seriousness (see Section 9.5.1.5.2 for the definition of an SAE).

Assessing Relationship to Study Treatment

Items to be considered when assessing the relationship of an AE to the study treatment are:

- Temporal relationship of the onset of the event to the initiation of the study treatment
- The course of the event, especially the effect of discontinuation of study treatment or reintroduction of study treatment, as applicable
- Whether the event is known to be associated with the study treatment or with other similar treatments
- The presence of risk factors in the study subject known to increase the occurrence of the event
- The presence of nonstudy, treatment-related factors that are known to be associated with the occurrence of the event

Classification of Causality

The relationship of each AE to the study drug will be recorded on the CRF in response to the following question:

Is there a reasonable possibility that the study drug caused the AE?

Yes (related) A causal relationship between the study drug and the AE is a reasonable possibility.

No (not related) A causal relationship between the study drug and the AE is not a reasonable possibility.

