With lemborexant as the only pharmacologically active moiety, the primary PK endpoints for the study will be the total C_{max} and AUC parameters for lemborexant, whereas the PK comparisons for the metabolites will be secondary endpoints. In order to account for potential prolongation of the half-life of lemborexant or metabolites in subjects with liver impairment, the PK samples will be collected up to Day 14 after dosing. One of the key assessments stipulated in all regulatory guidelines for special population studies (ie, renal and hepatic impairment) is the evaluation of any change in the unbound fraction of the pharmacologically active moieties in vivo and assessment of the relationship between the unbound plasma exposures (AUC_u) and apparent clearance with measures of liver impairment, where binding of the drug to plasma proteins is high (eg. >90%). With lemborexant and its main metabolites (M4, M9, and M10), plasma protein binding based on in vitro studies is approximately 88%, 74%, 86%, and 92% bound to human plasma, respectively, and linear over the clinically observed concentrations. Due to the marginally high plasma protein binding of lemborexant and its metabolites in the current study, 2 blood samples will be collected, one at the maximum plasma exposure time and one at trough level. The respective unbound PK parameters for lemborexant will be derived by applying the unbound ratio to the PK parameters calculated using total plasma concentrations of lemborexant. Plasma protein binding of metabolites will be assessed to compare these results to in vitro data and assess any difference between hepatic impaired subjects and healthy volunteers that is currently not anticipated. The analysis of the unbound PK parameters (lemborexant only) between subjects with liver impairment and normal controls will be considered as secondary PK parameter endpoints only.

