8.2 Secondary Objectives

The secondary objectives are:

- To evaluate the effects of hepatic impairment on the PK of lemborexant metabolites M4, M9, and M10.
- To evaluate the relationship between the PK parameters of lemborexant and its metabolites and the Child-Pugh Classification score, serum albumin, total bilirubin, and prothrombin time.

• To assess safety and tolerability of lemborexant following a single dose administration in subjects with mild and moderate hepatic impairment and healthy subjects.

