9 INVESTIGATIONAL PLAN

9.1 Overall Study Design and Plan

E2006-A001-104 is a multicenter, single dose, open-label, parallel-group study in subjects with mild and moderate hepatic impairment and matched (with regard to age [± 10 years], sex, and body mass index [BMI, $\pm 20\%$]) healthy control subjects. The study will enroll a total of 24 subjects, including 16 subjects with impaired hepatic function; 8 subjects each in Child-Pugh class A (mild) and B (moderate). At least 8 healthy subjects will be dosed as one control cohort to match (1:1) to the subjects with hepatic impairment in each Child-Pugh class with regard to age, sex, and BMI.

The study will consist of 2 phases: Prerandomization and Treatment. The Prerandomization Phase will include 2 study periods; Screening and Baseline (Day -1). The subjects will be admitted to the clinical facility on Day -1, remain confined to the clinic until Day 8, and then return to the clinical facility for additional PK sampling as outpatients until Day 14. In the event of early discontinuation of the subjects, the subjects with Child Pugh Class A and B (Cohorts A and B) and the matched controls (Cohort C) may be replaced.

On Day 1, the subjects will be administered a single 10-mg dose of lemborexant with approximately 240 mL of water in the morning after an overnight fast. The blood samples for PK assessments will be collected at prespecified intervals up to 312 hours postdose administration. The subjects will be discharged on Day 14 of the study. In addition, the blood samples for plasma protein binding assessments of lemborexant will be collected from each subject at 2 time points; approximately 1 hour and 24 hours postdose.

The end of the study will be the date of the last study visit for the last subject.

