- e: Subjects will fast for at least 4 hours before blood is drawn for clinical laboratory assessments. Measurement of serum albumin and creatinine will be part of the central laboratory tests. (revised per Amendment 01)
- f: Blood samples (4 mL per time point) for PK assessments will be collected on Day 1 (predose and at 0.5, 1, 1.5, 2, 3, 4, 6, 8, and 12 hours postdose), Days 2 (24 hours postdose), 3 (48 hours postdose), 4 (72 hours postdose), 5 (96 hours postdose), 6 (120 hours postdose), 7 (144 hours postdose), 8 (168 hours postdose), 10 (216 hours postdose), 12 (264 hours postdose) and 14 (312 hours postdose). If a subject is early terminated, he or she will not have a blood sample collected for PK unless early termination coincides with a scheduled PK time point. A variance of ±5 minutes (up to the first 2 hours postdose), ±10 minutes for time points up to, and including, Day 8 (168 hours postdose) and ±2 hours for Day 10 (216 hours postdose) to Day 14 (312 hours postdose) is allowed.
- g: Blood samples (12 mL per time point) for plasma protein binding will be collected at approximately 1 and 24 hours postdose, matching with the time collection for PK samples for lemborexant and its main metabolite, M4, M9 and M10.
- h: A single 10-mg dose of lemborexant as 1×10 mg tablet will be administered with 240 mL of water following an overnight fast. Dosing will be in the morning followed by a 4-hour postdose fast. Water will be allowed ad libitum except for the interval from 1 hour before to 1 hour after study drug administration.
- i: Subjects will be released from the clinic after completing the Day 8 procedures and then return to the clinic for outpatient visits on Days 10, 12, and 14.
- j: Subject will be released from the study after completion of Day 14 (end-of-study) procedures or early termination.

Table 5	ble 5 Blood Sampling Schedule for Pharmacokinetic Assessments					
Study day	Time (on each day) Acceptable time-window					
Day 1	Predose and at 0.5, 1, 1.5, 2, 3, 4, 6, 8, and 12 hours postdose	Predose; -1 hour Postdose (up to first 2 hours postdose); ±5 minutes				
		Postdose (after 2 hours postdose); ±10 minutes				
Day 2	24 hours postdose					
Day 3	48 hours postdose					
Day 4	72 hours postdose					
Day 5	96 hours postdose	±10 minutes				
Day 6	120 hours postdose					
Day 7	144 hours postdose					
Day 8	168 hours postdose					
Day 10	216 hours postdose					
Day 12	264 hours postdose	±2 hours				
Day 14	312 hours postdose					

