9.5.5 Completion/Discontinuation of Subjects

The investigator may withdraw the subject from the study at any time for safety or administrative reasons. A subject may elect to discontinue the study at any time for any reason. All subjects who discontinue the study are to complete the study's early discontinuation procedures indicated in the Schedule of Procedures/Assessments (Table 4).

The investigator will promptly explain to the subject involved that the study will be discontinued for that subject and provide appropriate medical treatment and other necessary measures for the subject. A subject who has ceased to return for visits will be followed up by mail, phone, or other means to gather information such as the reason for failure to return, the status of treatment compliance, the presence or absence of AEs, and clinical courses of signs and symptoms.

Subjects who discontinue early from the study will be discontinued for 1 of these primary reasons: AE(s), lost to follow-up, subject choice, withdrawal of consent, pregnancy, study terminated by sponsor, or other. In addition to the primary reason, the subject may indicate 1 or more of secondary reasons for discontinuation. Study disposition information will be collected on the Subject Disposition CRF.

A subject removed from the study for any reason may be replaced.

9.5.6 Confirmation of Medical Care by Another Physician (for Hepatic Impairment Subjects):

The investigator will instruct subjects to inform site personnel when they are planning to receive medical care by another physician. At each visit, the investigator will ask the subject whether he/she has received medical care by another physician since the last visit or is planning to do so in the future. When the subject is going to receive medical care by another physician, the investigator, with the consent of the subject, will inform the other physician that the subject is participating in the clinical study.

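### AEs are to be collected for 28 days after the single dose, but the schedule ends at Day 14, so completers have no scheduled contact for new-onset AEs in the last 15 days

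*Protocol*

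**What the plan says.** The collection duty is in Protocol 9.5.1.5.1. All AEs, whether or not related to drug or procedure, are covered for this period: "beginning from the time the subject signs the study ICF through the last visit in the Treatment Phase and for 28 days after". Those 28 days are counted from the last dose. The same section adds a duty for events already found: "All AEs must be followed for 28 days", or five half-lives if longer, or until resolution if that comes first.

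The schedule stops sooner. Table 4's last column is Day 14/early termination. Footnote i has subjects leave the clinic after Day 8 and "return to the clinic for outpatient visits on Days 10, 12, and 14". Footnote j then says: "Subject will be released from the study after completion of Day 14 (end-of-study) procedures or early termination". Section 9.1.2 sets the Treatment Phase at 14 days, and section 9.1 describes no follow-up phase and states: "The end of the study will be the date of the last study visit for the last subject".

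Remote contact appears once, in 9.5.5, and for a different group: "A subject who has ceased to return for visits will be followed up by mail, phone, or other means to gather information". It is not provided for subjects who attend every visit.

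Section 8.2 makes safety a secondary objective: "To assess safety and tolerability of lemborexant following a single dose administration in subjects with mild and moderate hepatic impairment", and in healthy subjects.

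**The concern.** A site that follows Table 4 exactly will not actively cover the AE window that 9.5.1.5.1 sets. After the Day 14 visit nobody is scheduled to ask a completer whether anything new has happened. An empty AE record for the period from Day 14 to Day 29 could therefore mean that no event occurred or that no one enquired, and the data could not tell these apart.

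The subjects in whom this could matter are the impaired ones. Section 7.2.3 extends PK sampling to Day 14 "In order to account for potential prolongation of the half-life of lemborexant or metabolites in subjects with liver impairment", and section 7.2.1 expects a large effect in moderate impairment. If exposure does persist beyond Day 14, it would be in those subjects. What is at stake is how complete late safety data are for a secondary objective. The primary comparison of Cmax and AUC does not depend on it.

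**Working it through.** **Inputs**
- Single dose on Day 1 (Protocol 9.1).
- AE collection to 28 days after the last dose (9.5.1.5.1).
- Last scheduled visit Day 14, nominally 312 h postdose, with a window of ±2 h (Table 4 footnote f, Table 5).
- 8 mild, 8 moderate and at least 8 healthy subjects (9.3).
- Terminal half-life about 45 to 55 h, 118 h with itraconazole, and effective half-life 16.9 to 39.3 h (7.1.1.2).

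**Reproducing the plan's timing.** Nominal hours = (study day − 1) × 24. Days 2, 3, 8, 10, 12 and 14 give 24, 48, 168, 216, 264 and 312 h, as Table 5 states. The SAP's study-day rule (6.2.5) also counts the dosing day as Day 1, so 28 days after dosing is Day 29.

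**Length of the gap**
- Last scheduled contact: 312 / 24 = 13 days postdose.
- Gap: 28 − 13 = 15 days, and 15 / 28 = 53.6% of the window.
- With the ±2 h visit window: 28 − 314/24 = 14.9 days to 28 − 310/24 = 15.1 days.

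**Subject-days without scheduled contact, if all complete**
- Moderate impairment: 8 × 15 = 120.
- All impaired: 16 × 15 = 240.
- Healthy controls: 8 × 15 = 120. The prolonged-exposure argument does not apply to these.

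**Drug remaining.** Terminal-phase fraction = 2^(−t / half-life).

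| Assumed half-life | Day 14 (312 h) | Day 29 (672 h) |
|---|---|---|
| 45 h | 0.8% | – |
| 55 h | 2.0% | – |
| 118 h | 16% | 1.9% |

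The documents give no half-life for impaired subjects. The 118 h row borrows the itraconazole result as an assumed upper case. The fractions describe the back-extrapolated terminal phase, not the peak. Because 7.1.1.2 reports less accumulation than the terminal half-life predicts, they probably overstate what remains relative to peak.

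**Routes open to a completer after Day 14**

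| Route | Scheduled? | Looks for new AEs? |
|---|---|---|
| Follow-up of AEs open at Day 14 (9.5.1.5.1) | No date set | No, known events only |
| Reporting of related SAEs without time limit (9.5.4.1) | No | No, relies on the investigator hearing of the event |
| Impaired subjects tell the site of care planned with another physician (9.5.6) | The investigator's question is asked at visits, which end at Day 14 | No |
| Unsolicited report by the subject | No | No |
| Mail or phone contact (9.5.5) | Only for subjects who stop attending | Not applicable to completers |

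**The case against.** The case for leaving the plan alone has substance. The protocol asks for AEs to be collected, not solicited at a dated contact, so receiving subject-reported events is compatible with its wording. Related SAEs must be reported however late they come to light, known AEs must be followed, and impaired subjects are told to mention care from other physicians. The dose is a single 10 mg; single doses up to 200 mg were generally well tolerated in healthy adults (7.1.1.2), and 7.2.3 regards the margins in impaired subjects as adequate. Subjects are confined until Day 8 and seen three more times, so peak and most exposure are observed. At the healthy half-life at least 98% of terminal-phase drug is gone by Day 14. Summary tables are limited to events emerging during treatment (9.7.1.8.2), a period not defined further, so it is unclear whether an event after Day 14 would reach a table.

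Most of this stands, and it keeps the consequence small. It does not remove the mismatch. Passive routes do not find new events, and the duty covers all AEs, not only serious or related ones. Whatever happens in the tables, 9.7.1.8.2 sends every AE to the subject listings, so late events would be reported if they were captured.

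Two limits of the reading also apply. The arrow in Table 4's Adverse Events row is not fully legible in the copy available, although no column lies beyond Day 14 and footnote j is explicit. The CRF Completion Guidelines, Investigator Study File, monitoring plan and consent pages were not available, so a site-level call may exist.

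**Conclusion.** The point holds as a mismatch between a stated duty and the schedule meant to deliver it. For completers, 15 of the 28 days after dosing have no scheduled contact for new-onset AEs. The effect is on completeness of late safety data, chiefly in the 16 impaired subjects (240 subject-days, 120 of them moderate), and it matters clinically only if half-life is prolonged there. It is worth correcting because correction is cheap, not because the study's conclusions are in doubt.

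A reader might infer more than the documents support:
- That all 360 of 672 subject-days (24 × 15 and 24 × 28) are at equal risk. One third of the 360 belongs to healthy controls, and 54% is calendar time, not exposure-weighted time.
- That about 16% of drug will remain at Day 14 in impaired subjects. This rests on a half-life seen with a strong inhibitor, not in liver impairment.
- That late AEs will be missed. The plan lacks a scheduled means of finding them; other routes may still bring them in.
- That primary PK is compromised. Sampling to 312 h and its analysis do not depend on contact after Day 14.

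The result assumes subjects complete to Day 14. An early terminator who has no further contact would have a longer gap.

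**What to change.** Add one remote AE/SAE contact per subject at about Day 29 as a new column in Table 4, and revise footnote j so that release from the study follows that contact rather than the Day 14 procedures. Section 9.1 should then say whether the contact counts as the last study visit when the end of study is defined. The same call can close out AEs open at Day 14 and cover the 28-day pregnancy reporting period in 9.5.4.2.

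The cost is about 24 calls, plus one for each replaced subject, with no added clinic visit or blood sample. It needs a written amendment (section 11), with IRB/IEC review unless the change is classed as logistical or administrative (5.1). The last contact moves up to 15 days later: 17 + 15/7 = 19.1, so about 17 weeks becomes about 19, and database lock may move with it.

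Cutting the collection window to Day 14 would also remove the inconsistency, but by giving up coverage in the subjects whose exposure could last longest. A discharge instruction asking subjects to report new events would be cheaper still, but it remains passive.
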